Corresponds to day-to-day reporting entry for crying time reported in minutes. Parents are asked to record their infants crying time to the nearest 5 minutes over 24 hours for 14 days. Each day starts at 6AM and finished the next day at the same time. Data is entered for each time slot separately. Each daily total is then compared to an independent day to day data entry (pseudo-double data entry). If daily sums do not match, the data is verified again, and errors are corrected. Data cleaning includes removing entries that would account for more than 24h of daily crying, reporting crying days from the day the first treatment was provided, transforming data when necessary (ex. 5 minutes time slots reported, graphical representation of crying time), replacing negative values or non-explicit string entries by missing values. Values are entered as minutes. Missing data is entered as blanks.

If some parents only report the daily total, these are to be recorded on a separate file (diary2.csv).

CastorEDC entries

Data is exported from the CastorEDC entry system from three separate forms:

1. *Baseline questionnaire (participant self report ; 24 questions)*
2. *Follow up questionnaire at 14 days post randomisation (participant self report, 27 questions)*
3. *Consultation information (osteopath reporting after each encounter)*

Data cleaning will be performed by the trial statistician consultation with the data manager

3. Datasets for data analysis

Six separate datasets are to be prepared.

1. *Merged data from Castor EDC (one line per participant)*

Dataset name: castor.csv

Source: CastrorEDC Baseline questionnaire (bq), follow-up questionnaire (fq) and consultation information (oq)

Format: csv

Details for data format

| Variable | Source | Description | Type | Levels |
|-------------|------------|--|-------------|--|
| id | bq, fq, oq | UID | Numerical | Nominal |
| pract | bq, oq | Practitioner | Numerical | Nominal |
| date_b | bq1.1 | Date of entry | Date | |
| date_end | fq1.1 | Date of last visit | Date | |
| parent_rel1 | bq1.2 | Relation to child for person answering 1 st questionnaire | Nominal | 1= mother, 2= father, 3=legal guardian, 4= other |
| parent_rel2 | fq1.2 | Relation to child for person answering 2 nd questionnaire | Nominal | 1= mother, 2= father, 3=legal guardian, 4= other |
| age | bq1.3 | Infant age (days) | Continuous | Days |
| bw | oq3.1 | Birth weight (Kg) | Continuous | Kg |

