| pharm7_txt | fq3.4.1 | Pharm & Supplements | Open text | String |
| help_belief_end | fq3.6 | Help belief at day 14 | Dichotomous | 0=no, 1=yes |
| experience_end | fq4.1 | Experience at day 14 | Ordinal | 1= very good, 2=fairly good, 3=neither good nor bad, 4=fairly poor, 5=very poor |
| satisfaction_end | fq4.2 | Satisfaction | Ordinal | 1=very satisfied, 2=fairly satisfied, 3=Neither satisfied nor dissatisfied, 4=fairly dissatisfied, 5=very dissatisfied |
| allocation_guess | fq4.3 | Participant's guess about allocation | Nominal | 0=Control treatment (TTR), 1=Test treatment (GTR), 2=Don't know/unsure |

2. Diary and group allocation entries

Dataset name: group.csv (one line per participant)

Source: Castor & Main investigator

Format: csv

- Group allocation is named A and B without the statistician knowing which group is which until after the analysis is complete.
- Per protocol analysis is completed from the detailed description of each deviation.

Details for data format

| Variable | Source | Description | Type | Levels |
|---------------|------------------------|--|-------------|-----------------------------|
| id | diary | UID | Numerical | integer |
| pilot | Data manager | Origin of the data | Dichotomous | 0=Main trial, 1=Pilot phase |
| group | Castor ECD | Group allocation | Dichotomous | Blinded to statistician |
| perprotocol | Participant log | Management was in accordance to protocol | Bi-nomial | 0=No, 1=Yes |
| deviation_txt | Principle investigator | Text description of protocol deviation | String | |

Dataset name: diary.csv (one line per day per participant)

Source: Crying diaries, crude data reported hourly

Format: csv

Details for data format

| Variable | Source | Description | Type | Levels |
|----------|--------|--|------------|---------|
| id | diary | UID | Numerical | integer |
| h6 | diary | Crying time from 6AM to 7AM (mins) | Continuous | minutes |
| h7 | diary | Crying time from 7AM to 8AM (mins) | Continuous | minutes |
| h8 | diary | Crying time from 8AM to 9AM (mins) | Continuous | minutes |
| h9 | diary | Crying time from 9AM to 10AM (mins) | Continuous | minutes |
| h10 | diary | Crying time from 10AM to 11AM (mins) | Continuous | minutes |
| h11 | diary | Crying time from 11AM to 7AM (mins) | Continuous | minutes |
| h12 | diary | Crying time from 12AM to 7AM (mins) | Continuous | minutes |
| h13 | diary | Crying time from 1PM to 2PM (mins) | Continuous | minutes |

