| h14 | diary | Crying time from 2PM to 3PM (mins) | Continuous | minutes |
| h15 | diary | Crying time from 3PM to 4PM (mins) | Continuous | minutes |
| h16 | diary | Crying time from 4PM to 5PM (mins) | Continuous | minutes |
| h17 | diary | Crying time from 5PM to 6PM (mins) | Continuous | minutes |
| h18 | diary | Crying time from 6PM to 7PM (mins) | Continuous | minutes |
| h19 | diary | Crying time from 7PM to 8PM (mins) | Continuous | minutes |
| h20 | diary | Crying time from 8PM to 9PM (mins) | Continuous | minutes |
| h21 | diary | Crying time from 9PM to 10PM (mins) | Continuous | minutes |
| h22 | diary | Crying time from 10PM to 11PM (mins) | Continuous | minutes |
| h23 | diary | Crying time from 11PM to midnight (mins) | Continuous | minutes |
| h24 | diary | Crying time from midnight to 1AM (mins) | Continuous | minutes |
| d14 | diary | Crying time from 1AM to 2AM (mins) | Continuous | minutes |
| d13 | diary | Crying time from 2AM to 3AM (mins) | Continuous | minutes |
| d14 | diary | Crying time from 3AM to 4AM (mins) | Continuous | Minutes |
| d13 | diary | Crying time from 4AM to 5AM (mins) | Continuous | minutes |
| missing | diary | Number of missing time slots | Continuous | Count |

Dataset name: diary2.csv (one line per participant)
Source: Crying diaries with only summary daily crying time
Format: csv

Details for data format

| Variable | Source | Description | Type | Levels |
|----------|--------|---|------------|---------|
| id | diary | UID | Numerical | integer |
| d0 | diary | Crying time day before treatment (mins) | Continuous | minutes |
| d1 | diary | Crying time on day of treatment (mins) | Continuous | minutes |
| d2 | diary | Crying time day 1 after treatment (mins) | Continuous | minutes |
| d3 | diary | Crying time day 2 after treatment (mins) | Continuous | minutes |
| d4 | diary | Crying time day 3 after treatment (mins) | Continuous | minutes |
| d5 | diary | Crying time day 4 after treatment (mins) | Continuous | minutes |
| d6 | diary | Crying time day 5 after treatment (mins) | Continuous | minutes |
| d7 | diary | Crying time day 6 after treatment (mins) | Continuous | minutes |
| d8 | diary | Crying time day 7 after treatment (mins) | Continuous | minutes |
| d9 | diary | Crying time day 8 after treatment (mins) | Continuous | minutes |
| d10 | diary | Crying time day 9 after treatment (mins) | Continuous | minutes |
| d11 | diary | Crying time day 10 after treatment (mins) | Continuous | minutes |

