Statistical blinding will be assured to generate summary variables and set the final analysis for between group differences. Once the final statistical coding is defined and validated by the TSC, the true group identity will be revealed and additional descriptive information on treatment will be provided.

- Coding allocation to random A, B to blind first step of statistical analysis
- Treatment description included in separate dataset to be coded with different IDS than main dataset.

5. Outcome measures

Primary Outcome measure

Crying time diary

The main outcome is daily crying time in minutes. This can be measured for crying times from the first day after treatment to the thirteenth day after treatment. Daily crying time is obtained by adding hourly reported crying times from 6AM to 5:59AM the next day. D-1 is computed from the hourly reported crying time on the day prior to the treatment if the entire day is completed. When incomplete, it is replaced by the parent reported 24h baseline crying time (castor.csv). Daily crying time is considered as missing if any of the time hour slots has missing values within the day.

The primary outcome is the between group average difference in crying time from day 1 after the treatment to day 13 after the treatment. Repeated measures random linear mixed effect adjusting for baseline crying time, expectations for treatment outcome and infant's age is used to estimate the between group difference.

If diaries only report the presence of crying during each hour slot, then each time slot is replaced by the corresponding median reported crying time for infants that were crying during that hour on that specific day of follow-up.

Secondary Outcome measure

Parent Confidence

Changes of parent confidence will be measured using the Parent Confidence Score at baseline and 14 day follow up. This score relies on 15 questions about parenting confidence with a likert scale of 4 choices (0 to 45 points). Changes over time will be measured at an individual level by adding the baseline value as a dependant variable in the mixed effect model. Movement of 6 points or more is to be considered as meaningful.

Global change

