- Analyse potential correlations between missing data in diary and overall summary measures.

Missing data for hourly entries will not be replaced (e.i. not missing total at random) unless parents did not report minutes in an explicit was. Graphical representations are replaced by estimates of hourly crying time. Reported crying within a hourly time slot without specification on the duration is replaced by the median observed crying time from other reported crying for that specific time slot (i.e. hour of the day and day of the trial).

Given the nature of the analysis, missing data within the diary will only reduce the power but should not affect the overall analysis.

For a diary to be considered, at least 7/14 days need to be filled in. Furthermore, best-case, and worst-case scenario will be simulated for the primary outcome implementing lowest and highest values for missing data (see sensitivity analysis).

Descriptive analysis

Descriptive statistics will be used to summarise the characteristics of participants in each arm of the trial. This will include baseline values, treatment schedules, compliance and follow-up. We will show number and percentage or mean and standard deviation for categorical and normally distributed continuous variables respectively. For data severely deviating from a normal distribution, we will present median and interquartile ranges. Probability of observed between groups difference will be provided using either Fisher's exact test, Chi2 test, and or Student's t-test.

Primary outcome analysis

We will analyse the primary outcome of crying time (e.i. individual daily measures of mean crying time in minutes) using random-effects multilevel linear regression. Crying time will be entered as the response variable (dependant) and the link function is identity. Therefore, lack of independence for measures from the same participant will be accounted for. To improve statistical power, the following explanatory variables are to be added to improve the modelling of the between-group differences

- baseline crying time (continuous),
- expectations from treatment (ordinal)
- and age of infants at entry (continuous).

To account for missing data, the data can be categorized and treated as nominal.

Results will be reported as between group difference in crying time in minutes with a 95% confidence interval. Statistical inference for significance of effects of the intervention will be calculated using Wald Chi² test.

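### Crying slots without minutes are filled with one median pooled over both arms, then summed and analysed as observed data for a mean difference

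*SAP*

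**What the plan says.** SAP section 5 (Crying time diary) builds the primary outcome as a sum: "Daily crying time is obtained by adding hourly reported crying times from 6AM to 5:59AM the next day". For diaries that mark only whether the infant cried in an hour, "each time slot is replaced by the corresponding median reported crying time for infants that were crying during that hour", taken from the same day of follow-up. Section 8 (Missing data) gives the same rule for any slot marked as crying without a duration: it is "replaced by the median observed crying time from other reported crying for that specific time slot". Neither place splits the donors by arm.

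Section 8 (Primary outcome analysis) enters the daily totals in a random-effects linear regression with identity link. It reports the between-group difference in minutes with a 95% confidence interval and a Wald test. No step carries the uncertainty of filled slots into that interval.

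Three other rules bear on the point:
- Section 5 sets a day to missing if any hour slot is missing.
- Section 8 admits a diary only if at least 7 of 14 days are filled in.
- Section 8 (Complementary confirmatory analysis) plans a rerun without the filled medians.

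On the file itself, section 2 says of the diary day: "Each day starts at 6AM and finished the next day at the same time". The diary.csv table in section 3 runs from "Crying time from 6AM to 7AM (mins" to "Crying time from 4AM to 5AM (mins".

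**The concern.** The fill-in aims at a different quantity from the analysis. The outcome is a total and the estimate is a difference in means, so a fill-in should preserve the expected minutes in the slot. A median does so only when its distribution has equal mean and median.

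The pooled value also carries no information about arm. If one treatment shortens crying within an hour without changing how many hours contain crying, a diary filled this way cannot show it. The filled numbers are constants for a given hour and day, yet the model treats them as measurements.

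The primary estimate and its confidence interval are at stake, to a degree that depends on how many slots are filled. The SAP does not say how many that is.

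**Working it through.** **1. Median against mean in a sum.** If k slots of a day are filled, the expected error in that day's total is k × (median − mean), with both taken among crying infants in the slot. Section 2 has minutes recorded to the nearest 5, and an hour slot cannot exceed 60. The SAP gives no distribution, so the shapes below are assumptions on the grid 5, 10, …, 60.

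| Assumed minutes per crying slot | Mean | Median | Median − mean |
|---|---|---|---|
| Right-skewed, truncated exponential, scale 15 | 16.52 | 15 | −1.52 |
| Right-skewed, truncated exponential, scale 25 | 21.6 | 20 | −1.6 |
| Uniform | 32.5 | 32.5 | 0 |
| Left-skewed, mirror image of scale 25 | 43.4 | 45 | +1.6 |
| Left-skewed, mirror image of scale 15 | 48.48 | 50 | +1.52 |
| 45% scale 15, 55% recorded as a full hour | 40.43 | 60 | +19.57 |

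The last mean is 0.45 × 16.52 + 0.55 × 60 = 40.43. The sign changes with the shape.

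**2. Effect on the difference through level.** If an affected diary shifts by b minutes a day, and shares pA and pB of the diaries are affected, the difference shifts by b × (pA − pB). With equal shares this is 0. The cancellation is not exact, because b grows with the number of filled slots and that number may itself differ by arm.

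**3. Effect on the difference through pooling.** Write a daily total as N crying slots times m minutes per slot. The true difference between arms is N1·m1 − N2·m2. In diaries filled throughout with a common value m*, it becomes (N1 − N2)·m*. Section 7 plans on a mean of 120 minutes and a difference of 30. As an illustration, let the control total be 8 × 15 = 120.
- Fewer crying hours in the test arm: 6 × 15 = 90. Filled with m* = 15, the difference is (8 − 6) × 15 = 30 and is kept.
- Shorter crying per hour in the test arm: 8 × 11.25 = 90. Filled with any common value, the difference is (8 − 8) × m* = 0 and is lost.

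If 10% of diaries in each arm were filled throughout (an assumed share), the second case would give 0.9 × 30 + 0.1 × 0 = 27 minutes and the first would stay at 30.

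**4. What the rerun without fill-in compares.** Without the fill-in, every day with such a slot becomes missing. A diary with these slots on 8 days keeps 14 − 8 = 6 days, below the required 7. A diary that never gives minutes has no usable crying day. The rerun therefore changes which infants are analysed as well as how slots are handled.

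**5. Slot count in diary.csv.** h6 to h24 is 24 − 6 + 1 = 19 rows. Four rows follow, from 1AM to 5AM, so there are 23 against the 24 that sections 2 and 5 require. The four night rows use the names d14 and d13 twice each, giving 19 + 2 = 21 distinct names. No row covers 5-6AM.

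**The case against.** The best defence is that the rule is small, robust and already checked. A pooled median resists outliers in thin cells. At 120 minutes a day and an assumed 18.4 minutes per crying slot, 120 / 18.4 = 6.5 of 24 slots contain crying, or 27%. With 48 infants per arm that is about 13 donors per arm for an average hour and day, and fewer in quiet hours. Parents are blinded, so nothing suggests that one arm would have more such slots. Arm differences in the number of crying hours survive. A rerun without the medians is planned.

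Much of this stands. It limits the size of the problem, and it argues against simply swapping in a mean for each hour, day and arm: that would thin the donors and still treat fill-ins as exact. It does not rescue the rule, because the loss of arm information and the understated uncertainty remain. The rerun cannot isolate the rule either, since it drops wholly presence-only diaries.

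Four stronger readings are tempting, and the SAP does not support them:
- **Totals are built too low.** The planning mean makes right skew plausible: the mean per crying slot exceeds 30 minutes only if crying falls in fewer than 120 / 30 = 4 hours a day. But the SAP gives neither the number of crying hours nor the distribution within them.
- **The error rivals the 30-minute target.** That sets a shift within one affected diary against a difference between arms, and it requires every crying slot to be filled.
- **The analysis uses 23-hour days.** The explicit 24-hour definition governs. The table is visibly faulty (one row reads "Crying time from 11AM to 7AM (mins"), a row lost in PDF extraction cannot be fully excluded, and the comparison with independently entered daily totals in section 2 could expose a dropped hour.
- **diary2.csv shifts the follow-up window.** Its column descriptions already mark one column as "Crying time on day of treatment (mins" and place days 1 to 13 after treatment in d2 to d14.

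**Conclusion.** The concern holds as a flaw in how the fill-in is fixed; it does not establish a bias of known direction. The pooled median does not in general preserve the mean daily total, removes arm differences in minutes per filled slot, and leaves imputation uncertainty out of the standard errors.

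The last two faults follow from the rule whatever the skew. The sign and size of the first rest entirely on the assumed shapes in the table. The effect on the trial's estimate depends on the share of filled slots and its balance between arms, neither of which is stated. With few filled slots, evenly spread, the effect would be small. This is a cheap improvement to the primary analysis and no ground for calling the planned result invalid.

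The missing 5-6AM row is a minor codebook contradiction.

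**What to change.** In the primary analysis, replace the median with multiple imputation of minutes in slots marked as crying. Bound the values at 60 and condition on hour, day of follow-up, blinded arm (A/B) and the infant's other data, such as the number of crying slots, baseline crying time and age. Sum within each completed dataset, fit the planned model and pool the results with Rubin's rules. Using the A/B code keeps the statistician blinded.

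Report the number of imputed slots and affected diaries by arm. Keep the pooled median as a sensitivity analysis. Keep the planned rerun without imputation as well, with a note that it drops wholly presence-only diaries.

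In section 3, list all 24 hourly slots of diary.csv with unique names, including 5-6AM, and correct the h11 and h12 descriptions, so that the table matches the day defined in sections 2 and 5.

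The cost is SAP and code wording, a little more analysis work, and reliance on an imputation model. For diaries with no minutes at all, that model must assume that their crying slots resemble those of comparable infants in the same arm.

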1. Description of study

Background:

Infants who excessively cry, are distressed and unsettled can have a marked impact on family life. Around 1 in 6 families are affected, it is associated with maternal depression, anxiety and loss of parenting confidence. These infant behaviors are usually self-limiting (subsiding around 12 weeks after birth) but during this difficult period many parents look for additional support. There is limited research and therefore much debate about the effectiveness of manual therapy and osteopathic care for these infants.

Aim:

To evaluate the effectiveness and healthcare cost of osteopathic care for excessively crying, unsettled and distressed infants (< 10 weeks old).

[figure not shown]
Study design:

[figure not shown]
A two-arm pragmatic randomised controlled trial to assess the effectiveness of osteopathic manual therapy on infant crying time. We will need to randomize 112 parent(s)/carers and their infants to either: i) Osteopathic manual therapy with best usual care advice and support or, ii) Light non-specific touch attention control (equal time spent with infant) with best usual care advice and support. Parents will be blinded to whether their infant receives the manual therapy care or not. The cost of the delivery of the intervention will be determined and compared with data about the cost of other care.

Population: Healthy infants under 10 weeks old, reported by their parent(s)/carers as excessively crying, unsettled and distressed and difficult to console using the Rome IV criteria (> 3 hours of crying per day, for 3 days for 1 week or more). Infants with diagnosed health conditions for which they are receiving medical treatment, or who would not normally be suitable for osteopathic treatment will be excluded from the study.

Outcomes: The primary outcome is reduced average daily infant crying time over 14 days, collected via parent reported diaries. Secondary outcomes are: i) Parental self-efficacy ii) Parent perceived global improvement iii) Satisfaction and experience with treatment and iv) Adverse events.

Diagram 1. Study scheme flow chart

2. Source documents

Crying diary (participant self-report)

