This question asks about overall change in the infant's symptoms, from completely recovered to vastly worse. (Completely recovered, much improved, slightly improved, no change, slightly worse, much worse, vastly worse). These levels are coded numerically in an ordinal manner and are to be compared between groups using non-parametrical approaches.

Experience and satisfaction

Experience was measured using a 5-point likert scale from Very good, fairly good, neither good not bad, fairly poor and very poor.

Satisfaction was measured using a 5-point likert scale from Very satisfied, fairly satisfied, neither satisfied nor dissatisfied, fairly dissatisfied and very dissatisfied.

We also asked if the parent thought osteopathic care helped their baby using a yes, no or unsure response.

Unexpected and or Adverse events

We asked parents about additional care they may have administered to their infants and additional health care consultations they sought during the trial period as a proxy indicator of adverse events, and we also asked directly about any changes in symptoms that cause the parent concern. These included more distress, more crying, more unsettled, more vomiting, increased difficulty in feeding, sleeping and anything else (other).

Serious adverse events are reported by parents and managing osteopaths. These are assessed by the trial managing group and coded as for the reason for being a SAE and the estimated likelihood these are related to the treatment.

6. Randomisation

Block randomisation with variable block size of 4 and 6 generated by CastorEDC.

7. Sample size

From data collected during the pilot phase (n=13), we confirmed crying times as expected by Wolke et al. We estimate the average daily crying time over the two-week follow-up period to be of 120 minutes with a SD of 45 minutes. To detect a minimum of 30 minutes additional reduction in crying time between the intervention and control group with 90% power and a two-sided 5% significance level we would need 48 infants in each arm of the trial. If we allow for a 15% drop out we would need to randomise 112 infants, 66 in each arm of the trial. This sample size calculation is conservative because it disregards the fact that there are repeated measures in each infant and that the model will be corrected for the baseline crying time value. Thus, the actual power will be higher.

| Power | MCID (daily reduction in crying time in minutes) | | | |

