|--------------|---|-----------|-----------|-----------|
| | 10 | 15 | 30 | 60 |
| 0.8 | 636 | 284 | 72 | 18 |
| 0.9 | 852 | 380 | 96 | 24 |
| 0.95 | 1054 | 468 | 118 | 30 |

Table 4 : Sample size estimates without loss to follow up.

8. Statistical Analysis

All analysis will be intent-to-treat except for a secondary per protocol analysis on the primary outcome. All *P* values will be two sided, and the significance level is set at 5%. We will use STATA15 to precode the entire analysis prior to data collection (.do file). Deviations from the initial statistical plan will be recorded on the statistical output report.

Computing new variables

Protocol deviation

A new variable will be computed to identify deviations from protocol. Any participant who dropped-out, missed out a planned treatment, received external osteopathic care during the follow-up, or did not complete the diary daily are considered as participants who deviated from the protocol.

Unexpected reactions and adverse events

Serious adverse events, sae, will be reported as a total number for each group and as a risk ratio.

Serious adverse events will be monitored throughout the trial and reported by either the osteopaths or the participant parent.

Detailed reporting of unexpected reactions from follow-up and from the follow-up questionnaire are to be summarised to describe the presence of any unexpected reactions during the follow-up period.

Treatment description

A new set of variables is to be merged from detailed description of treatments during each visit and summarize whether each subset of care was provided or not.

Parent confidence scale

Parent confidence scale at baseline (pcs_b) and at 14 days (pcs_e) are computed from the 15 individual questions. Likert scales are scored 0 to 3 points. Scores for Q13 are inverted. Values for not applicable in Q1 and Q9 are given the score of 2. The points are then added up.

For descriptive purposes, the parent confidence scale at baseline can be compared with the following ranges:

- Non-clinical range 40 or more
- Mild clinical range 36-39
- Moderate clinical range 31-35
- Severe clinical range 31 or less

Missing data

Where participants withdraw, we will compare the characteristics of those withdrawing against those who remain in the study. Furthermore, we will do an:

- overall descriptive analysis of missing data searching for patterns,
- compare between group differences in missing data,

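### SAP section 7 asks for 112 infants but 66 in each arm, which makes 132; on the plain reading of its SD, it also credits repeated measures with power already counted

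*SAP*

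**What the plan says.** SAP section 7 (Sample size) sets out the calculation as follows.

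- Outcome and spread: "We estimate the average daily crying time over the two-week follow-up period to be of 120 minutes with a SD of 45 minutes".
- Difference sought: "To detect a minimum of 30 minutes additional reduction in crying time between the intervention and control group". The test is two-sided at 5% and the power is 90%.
- Size before dropout: "we would need 48 infants in each arm of the trial". The sample size table in the same section gives a total of 96 for 30 minutes at power 0.9.
- Size after dropout: "If we allow for a 15% drop out we would need to randomise 112 infants, 66 in each arm of the trial".
- Comment on power: "This sample size calculation is conservative because it disregards the fact that there are repeated measures in each infant". The sentence adds correction for baseline crying time as a second reason, and the section concludes that true power will exceed the nominal figure.

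SAP section 1 (Study design) gives the total again: "We will need to randomize 112 parent(s)/carers and their infants". It gives no per-arm figure.

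**The concern.** The total and the per-arm number in the same sentence disagree. Achieved recruitment will be judged against this target and the trial report will quote it, so it has to be one number.

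The comment on power raises a separate question. If the SD describes each infant's average over the follow-up, the reduction in variance from recording many days is already inside it. Citing repeated measures as a further source of power then counts the same gain twice.

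**Working it through.** **Inputs (SAP section 7):** difference δ = 30 minutes; SD σ = 45 minutes; two-sided 5% (z = 1.96); 90% power (z = 1.2816); equal arms; 15% dropout.

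**1. The plan's own figure.** n per arm = 2(1.96 + 1.2816)² × 45² / 30² = 47.28, rounded up to 48, or 96 in total. This matches the text. The same normal-approximation formula reproduces all 12 cells of the sample size table.

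**2. Total against per-arm number.**
- 2 × 66 = 132
- 112 / 2 = 56
- 132 − 112 = 20 infants

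**3. Which number fits a 15% allowance.**
- Multiplying up: 48 × 1.15 = 55.2, so 56 per arm and 112 in total.
- Dividing by the retained fraction: 48 / 0.85 = 56.5, so 57 per arm and 114 in total.
- Neither gives 66. Applying the allowance a second time would, since 56 / 0.85 = 65.9. The origin of 66 therefore cannot be settled from the document.

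**4. Power after 15% dropout**, using power = Φ(δ / (σ√(2/n)) − 1.96):

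| Randomised per arm | Left per arm | Power |
|---|---|---|
| 56 | 47.6 | 90.2% |
| 66 | 56.1 | 94.2% |

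For comparison, 48 per arm gives 90.4%. A total of 112 leaves 112 × 0.85 = 95.2 infants against 96. It retains the full 96 up to a dropout of 1 − 96/112 = 14.3%.

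**5. Repeated measures.** The primary outcome in SAP section 5 is the between-group difference averaged over days 1 to 13. With complete, balanced diaries and a random intercept per infant, the mixed model's group effect equals the comparison of infant means. If 45 is the SD of those means, as worded, the daily records add no power beyond the 90.4% at 48 per arm.

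Suppose instead that 45 were a single-day SD (an assumption). With 13 days and within-infant correlation ρ, the SD of the mean is 45 × √((1 + 12ρ)/13):

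| ρ (assumed) | SD of mean (minutes) | Power at 48 per arm |
|---|---|---|
| 0.3 | 26.8 | 99.98% |
| 0.5 | 33.0 | 99.4% |
| 0.7 | 38.3 | 97.0% |
| 0.9 | 42.9 | 92.9% |

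On that reading the plan's argument would hold.

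**6. Baseline adjustment.** With baseline-to-follow-up correlation r, the SD becomes 45 × √(1 − r²). The plan gives no r. At assumed values of 0.3, 0.5 and 0.7, power at 48 per arm is 92.8%, 96.5% and 99.6%.

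**The case against.** The strongest defence is that 112 is not really in doubt. It is given twice as the number to randomise, it follows from 96 plus 15%, and 132 appears nowhere. No analysis or decision rule in the SAP uses 66. This stands as a reason to think 66 is the wrong figure. It does not remove the contradiction, and only the sponsor can confirm which number was meant.

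A reader might infer that the trial is under-sized because 112 less 15% falls below 96. The document does not support that. The shortfall is 0.8 of an infant, and power by the plan's own formula remains 90.2%. Multiplying by 1.15 rather than dividing by 0.85 costs two infants at most (112 against 114).

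A reader might also infer that the whole claim of higher power is wrong. That goes too far. Baseline crying time is in the primary model (SAP sections 5 and 8), and adjusting for it can raise power without help from the repeated measures. Only the repeated-measures reason is in question, and even that depends on what the 45 describes. The wording points to the two-week average but does not say outright that 45 is the between-infant SD of those averages.

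**Conclusion.** The point holds in two parts.

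- **Main part.** The total of 112 and the 66 per arm cannot both be right; they differ by 20 infants. That follows from the text without any assumption. That 66 is a slip for 56 is a probable inference, not a fact.
- **Secondary part.** On the plain reading of the SD, repeated measures add no further power and should not be given as a reason. This rests on 45 being the SD of the infant mean, and on complete diaries with a random-intercept model. The baseline reason stands, but the size of its gain is unknown because the plan gives no correlation.

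The basic calculation (48 per arm) and the nominal 90% power are unaffected.

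**What to change.** 1. State one consistent total and per-arm target in section 7, matching section 1. If 112 is intended, write 112 infants, 56 in each arm.
2. Optionally add that 112 covers about 14% dropout, and that about 90% power is still kept at 15%.
3. State whether 45 minutes is the SD of the infant's two-week mean or of a single day.
4. If it is the infant mean, remove the repeated-measures reason. Rest the expected gain on baseline adjustment alone, and say that its size depends on the baseline-to-follow-up correlation.

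The cost is a few lines of SAP wording. If 112 is confirmed, no further infants are needed, and the analysis does not change.
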